13.5 Anaphylaxis

A suspicion of anaphylaxis will be carefully monitored and treated according to standard of care. Emergency crash cart equipment and medications including multiple doses of epinephrine, vasopressors, and bronchodilators will be available at all times during the conduct of the study. To define anaphylactic reactions in a consistent and objective manner, all AE of suspected anaphylaxis will be evaluated using Sampson's Criteria for Anaphylaxis ([Appendix 10](#)). The assessment of an AE will be done pursuant to definitions set forth by ICH Good Clinical Practice guidelines and applicable regulatory requirements.

If a subject experiences signs or symptoms of anaphylaxis, the subject may be treated with standard of care such as diphenhydramine, acetaminophen, methylprednisolone, epinephrine, and other supportive measures along with cessation of the infusion.

13.6 Evaluating Adverse Events and Serious Adverse Events

13.6.1 Establishing Diagnosis

Whenever possible, diagnoses should be given when signs and symptoms are due to a common etiology (e.g., dysuria, urinary nitrites should be reported as a urinary tract infection). If the diagnosis is not known, individual signs and symptoms should be assessed and recorded in the Adverse Event eCRF as separate AE. The Investigator (or qualified Subinvestigator) must assign the following AE attributes listed below and is responsible for ensuring their capture in the source documentation.

13.6.2 Assessment of Intensity

The Investigator will use their clinical judgment as well as the guidelines laid out in the National Cancer Institute Common Terminology Criteria for Adverse Events (CTCAE) (Version 5.0 or most current version) ([Table 2](#) and [Appendix 8](#)) to assess the intensity of each AE and SAE.

Table 2 Adverse Event Severity per CTCAE

Grade	CTCAE Description*
1	Mild; asymptomatic or mild symptoms; clinical or diagnostic observations only; intervention not indicated.
2	Moderate; minimal, local or noninvasive intervention indicated; limiting age appropriate instrumental activities of daily living (ADL).
3	Severe or medically significant but not immediately life-threatening, hospitalization or prolongation of hospitalization indicated; disabling; limiting self-care ADL.
4	Life-threatening consequences, urgent intervention indicated.
5	Death related to adverse event.

* CTCAE version 5.0: Grade refers to the severity of the AE. The CTCAE displays Grades 1–5 with unique clinical descriptions of severity for each AE based on this general guideline.

The term “severe” is a measure of intensity, and a severe adverse event is not necessarily a serious adverse event (SAE).

When the intensity of an AE changes more than once a day, the maximum severity for the event should be entered into the AE eCRF. If the intensity changes over a number of days, these changes should be recorded separately (i.e., as having distinct onset dates).

13.6.3 Assessment of Causality to Study Drug

The Investigator should use their clinical judgment as well as the guidelines in Table 3 to assess the relationship between study drug and AE.

Table 3 Adverse Event Relationship to Study Drug

Relationship to Study Drug	Comment
Related	There is clear evidence that the event is related to the use of study drug (e.g., confirmation by positive re-challenge test, if possible). Another etiology is considerably less likely.
Possible	The event cannot be explained by the subject’s medical condition, concomitant therapy, or other causes, and there is a plausible temporal relationship between the event and study drug administration.
Unlikely/Remote	An event for which an alternative explanation is more likely (e.g., concomitant medications or ongoing medical conditions) or the temporal relationship to study drug administration and/or exposure suggests that a causal relationship is unlikely. (For reporting purposes, Unlikely/Remote will be grouped together with Not Related.)
Not Related	The event can be readily explained by the subject’s underlying medical condition, concomitant therapy, or other causes, and therefore, the Investigator believes no relationship exists between the event and study drug.

13.6.4 Assessment of Causality to Study Procedure

The Investigator should use their clinical judgment as well as the guidelines in Table 4 to assess the relationship between study procedure and AE. Assessment of Causality to Study Procedure should include causality to such items as EGD with biopsy or blood draw (as appropriate), or other.

Table 4 Adverse Event Relationship to Study Procedure

Relationship to Study Procedure	Comment
Related	There is clear evidence that the event is related to a study procedure.
Possible	The event cannot be explained by the subject's medical condition, concomitant therapy, or other causes, and there is a plausible temporal relationship between the event and a study procedure.
Unlikely/Remote	An event for which an alternative explanation is more likely (e.g., concomitant medications or ongoing medical conditions) or the temporal relationship to any study procedure suggests that a causal relationship is unlikely (For reporting purposes, Unlikely/Remote will be grouped together with Not Related).
Not Related	The event can be readily explained by the subject's underlying medical condition, concomitant therapy, or other causes, and therefore, the Investigator believes no relationship exists between the event and a study procedure.

13.6.5 Action Taken

Action taken with respect to study drug will be categorized as none, study drug permanently discontinued, study drug temporarily withdrawn, or other (specify).

Action taken with respect to study participation will be categorized as none, withdrawal from study participation, or other (specify).

Action taken with respect to treatment of an AE will be categorized as none, concomitant medication, concomitant procedure, or other (specify).

13.6.6 Assessment of Outcome

Event outcome at resolution or time of last follow-up will be recorded as recovered, recovering, not recovered, recovered with sequelae, fatal, or unknown.

13.7 Adverse Event Reporting Procedures

13.7.1 All Adverse Events

Any clinically significant AE that is ongoing at the time of study completion or early termination will be followed by the Investigator until event resolution, the AE is otherwise explained, not considered clinically significant by the Investigator, or the subject is lost to follow-up.

All AE identified, whether serious or non-serious, will be recorded in the Adverse Event eCRF beginning from the time of first study drug infusion and ending at the time of the Day 197 visit, the Day 372 visit (for subjects participating in the OLE period), or the ET visit, unless otherwise directed by Allakos. For subjects participating in the OLE period, AE will be assessed and recorded in the CRF of the AK002-014 treatment period database up until the start of the first open-label infusion during the Day 176 visit and recorded in the CRF of the AK002-014 OLE period database beginning from the start of the first open-label infusion during the Day 176 visit. Serious adverse events considered related to screening procedures will be recorded in the Adverse Event eCRF starting on the date of informed consent. Only AESI and SAE will be recorded in the Adverse Event eCRF during extended follow-up, if applicable. Whenever appropriate, the CTCAE (v. 5.0 or most current version) should be utilized for naming common AE ([Appendix 8](#)).

13.7.2 Serious Adverse Event Reporting

In the event of any SAE reported or observed during the study, whether or not attributable to the study drug, site personnel must report it immediately (**within 24 hours of becoming aware of the SAE**) by telephone or email to the Sponsor, Allakos Inc.

Serious adverse event report forms will be provided to the investigational site to assist in collecting, organizing, and reporting SAE, and forms must be completed with as much information as is available and should be submitted to the Sponsor within 24 hours of becoming aware of the event. The SAE must also be recorded on the Adverse Event eCRF and designated as “serious.”

Even when only minimal information is available for the initial SAE report, the Investigator should try to make a causality assessment, as the causality is used to determine the timing of regulatory reporting requirements. If the Investigator or designee is not available to sign the SAE report upon initial submission they should be contacted via telephone and their assessment documented on the SAE form (with a note stating signature is forthcoming). The Investigator **may change** the causality assessment based on follow-up information and submit an amended SAE report form.

All efforts will be made to obtain accurate and complete medical records for the SAE. All efforts to obtain information should be documented in the subject source document. The site will notify the Institutional Review Board (IRB) according to its guidelines.

The subject's condition will be followed by the Investigator or designated Subinvestigator until resolution of the condition or a return to baseline levels. If additional visits are required, the subject will be asked to return to the study site for further follow-up. If the condition is still ongoing at the time the subject exits the study, every effort will be made to continue to follow up with the subject for a reasonable period of time, as determined by the Investigator or until there is a return to Baseline or stabilization of the condition. As additional information becomes available, such as hospital discharge notes and patient medical records, the Investigator will be notified and provided with all relevant information.

All SAE that have not resolved by the end of the study or that have not resolved on discontinuation of the subject's participation in the study must be followed until any of the following occurs:

- The event resolves.
- The event stabilizes.
- The event returns to Baseline if a baseline value is available.
- The event can be attributed to agents other than the investigational product or to factors unrelated to study conduct.
- It becomes unlikely that any additional information can be obtained (subject's or health care practitioner's refusal to provide additional information, lost to follow-up after demonstration of due diligence with follow-up efforts).

Serious adverse events must be reported within 24 hours to:

SAE Reporting

[contact]

Email: [contact]

13.7.3 Pregnancy Reporting

Pregnancies are captured if they occur in female subjects or in the sexual partners of male subjects from the time the subject is first exposed to the investigational product through Day 141 (± 3 days), Day 316 (for subjects participating in the OLE period), or ET.

Female subjects must be instructed to discontinue all study drugs and inform the Investigator immediately if they become pregnant during the study. Male subjects must be instructed to inform the Investigator immediately if their partner becomes pregnant during the study.

The Investigator must report any pregnancy to Allakos within 24 hours of becoming aware of it using the provided pregnancy reporting forms. Female subjects must be immediately discontinued from study drug. An uncomplicated pregnancy will not be considered an AE or SAE, but all pregnancies will be followed through term.

Any congenital abnormalities noted at birth in the offspring of a subject who received study drug will be reported as an SAE. The outcome of any pregnancy and the presence or absence of any congenital abnormality will be recorded in the source documentation and reported to the Medical Monitor and Sponsor.

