4.5.3 Treatment

AK002 or placebo administered to subjects on Days 1, 29, 57, 85, 113, and 141.

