13.1 Adverse Events

In accordance with 21 Code of Federal Regulation (CFR) 312.32(b) and International Conference on Harmonisation (ICH) Guidance E2A, an adverse event is any untoward medical occurrence in a clinical investigation of a subject administered a pharmaceutical product and that does not necessarily have a causal relationship with the treatment. An AE is therefore any unfavorable and unintended sign (including an abnormal laboratory finding), symptom, or disease temporally associated with the administration of an investigational product, whether or not related to that investigational product. An unexpected AE is one of a type not identified in nature, severity, or frequency in the current Investigator's Brochure or of greater severity or frequency than expected based on the information in the Investigator's Brochure.

Examples of an AE include:

- Significant worsening or exacerbation of an underlying medical condition.
- Significant abnormal findings from physical exams, vital signs, or laboratory tests.

The following examples are not considered an AE:

- Medical or surgical procedure, although the condition leading to the procedure is usually an AE.
- Anticipated day-to-day fluctuations of preexisting medical conditions (including laboratory values) as long as significant worsening from Baseline does not occur.
- Signs or symptoms of the disorder being studied unless they become more severe or occur with a greater frequency than occurring at Baseline.

All AE, whether elicited by questions from study staff, volunteered, or noted on physical examination/laboratory testing, and regardless of causality or severity, will be assessed and recorded in the eCRF beginning after first administration of study drug and ending at the time of the Day 197 visit, the Day 372 visit (for subjects participating in the OLE period), or the ET visit, unless otherwise directed by Allakos. For subjects participating in the OLE period, AE will be assessed and recorded in the CRF of the AK002-014 treatment period database up until the start of the first open-label infusion during the Day 176 visit and recorded in the CRF of the

AK002-014 OLE period database beginning from the start of the first open-label infusion during the Day 176 visit.

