14.1 Definition of Study Completion

A subject who does not participate in the OLE period and who completes visits through the Day 197 visit or, if applicable, the last Extended Follow-Up visit after completing Day 197, will be recorded as having completed the double-blind portion of the study.

A subject who completes visits through the Day 169 visit and participates in the OLE period of the study will be recorded as having completed the double-blind portion of the study.

A subject who participates in the OLE period of the study and completes visits through the Day 372 visit or, if applicable, the last Extended Follow-Up visit after completing Day 372, will be recorded as having completed the OLE portion of the study.

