PK: Pharmacokinetics

Table 5 Notes

- 1) Refer to assessment footnote for specific timing (e.g., predose, during infusion, postdose).
- 2) The Investigator will evaluate whether the subject is eligible for the OLE period per Section 19.12.3. On Day 176 (± 3 days), eligible subjects that choose to participate in the OLE period will begin following the OLE Schedule of Events and will receive the first open-label AK002 infusion.
- 3) Subjects should complete the DSQ daily after the last meal of the day. If Question 1 is answered “No,” the subject should answer the Solid Food Question ([Appendix 2](#)) after the DSQ is completed and submitted. The site is responsible for monitoring compliance and discussing compliance during study visits.
- 4) **CCI** should be the first assessment completed by the subject at the beginning of the study visit prior to other assessments.
- 5) Per Inclusion Criterion #7, subjects should maintain the baseline diet consistently throughout the study. Diet compliance will be discussed during study visits and any variance will be documented.
- 6) Weight will be measured predose on Days 176, 204, 232, 260, 288, and 316, and Days 344 and 372 (or ET).
- 7) Vital signs will be measured at all OLE visits. On dosing days (Days 176, 204, 232, 260, 288, and 316), vital signs will be measured predose, 15 minutes (± 5 minutes) after infusion start, immediately postdose (within 5 minutes after infusion end), and 1 hour (± 5 minutes) postdose. Subject should be at rest for ≥ 5 minutes before vital signs (systolic and diastolic blood pressure, pulse, body temperature, and respiratory rate) are measured.
- 8) Please see the Central Laboratory Manual for collection, processing, and shipment instructions. Samples should be shipped on the same day as collection.
- 9) Blood for total serum IgE will be obtained predose on Day 316 and again on Day 372 (or ET).
- 10) Blood for CBC with differential will be obtained at all OLE period study visits. On Days 176, 204, 232, 260, 288, and 316, blood will be drawn twice (predose and 1-hour postdose).
- 11) Blood for chemistry will be obtained at all OLE period study visits. On Days 176, 204, 232, 260, 288, and 316, blood for chemistry will be drawn predose.
- 12) Blood for PK will be obtained at all OLE period study visits. On Days 176, 204, 232, 260, 288, and 316, blood for PK will be drawn predose.

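### Section 13.7.3 ends pregnancy capture on the nominal last-dose day, against its own reporting duties and 56 nominal days before the AE window closes

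*Protocol*

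**What the plan says.** Protocol section 13.7.3 opens by defining the capture period for pregnancies in female subjects and in partners of male subjects. It runs "from the time the subject is first exposed to the investigational product through Day 141" (±3 days), Day 316 for OLE subjects, or ET.

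Both days are last-dose days. Section 4.5.3 gives the double-blind schedule: "AK002 or placebo administered to subjects on Days 1, 29, 57, 85, 113, and 141". Table 5, note 7 gives the OLE schedule: "On dosing days (Days 176, 204, 232, 260, 288, and 316".

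The rest of 13.7.3 uses other limits, or none:

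- For partners: "Male subjects must be instructed to inform the Investigator immediately if their partner becomes pregnant during the study". Female subjects have a parallel instruction for their own pregnancies.
- For the site: "The Investigator must report any pregnancy to Allakos within 24 hours of becoming aware of it", with no end day.
- On classification and follow-up: "An uncomplicated pregnancy will not be considered an AE or SAE, but all pregnancies will be followed through term".

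Inclusion criterion 9 (section 7.3) adds that fertile men should contact the investigator about a suspected partner pregnancy throughout their participation. Section 14.1 counts a subject outside the OLE as completing the double-blind portion when that subject "completes visits through the Day 197 visit or, if applicable, the last Extended Follow-Up visit after completing Day 197". AE recording under section 13.1 begins after the first administration, "ending at the time of the Day 197 visit", the Day 372 visit for OLE subjects, or the ET visit.

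The SAP sets no pregnancy capture period. Its section 6.8 plans only a listing of pregnancy test results.

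**The concern.** A site told on Day 160 that a subject or partner has become pregnant finds one sentence placing the pregnancy outside the capture period and others requiring a report. The longer AE and SAE windows do not settle the matter for an uncomplicated pregnancy, because 13.7.3 says that it is neither.

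Capture matters because follow-up through term and recording of the outcome depend on the pregnancy being known. The last scheduled urine test is predose on Day 141 (section 11.4.4) or Day 316 (Table 5, note 17). After that, detection depends on what subjects tell the site. If sites apply the opening sentence literally, pregnancies beginning in the weeks after the last infusion could be missing from the exposure data.

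**Working it through.** The check is day arithmetic on the protocol's schedule.

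**Inputs**

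- End of pregnancy capture: Day 141, or Day 316 in the OLE (section 13.7.3).
- Last dose: Day 141 (section 4.5.3), or Day 316 (Table 5).
- End of AE recording: Day 197, or Day 372 in the OLE (section 13.1).
- Visit windows: ±3 days on dose 6, with ±7 accepted as no deviation (Table 1, note 35), and ±7 on Day 197 (Table 1).
- Stated follow-up: 8 weeks after the last dose (synopsis, Duration of Subject Participation).

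**Reproducing the schedule**

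- Double-blind dose 6: 1 + 5 × 28 = Day 141.
- OLE dose 6: 176 + 5 × 28 = Day 316.
- Follow-up: 197 − 141 = 56 days and 372 − 316 = 56 days. Each is 56 / 7 = 8 weeks, as the protocol states.

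**Post-dose capture for a subject who completes dosing and the study**

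- Double-blind: 141 − 141 = 0 days.
- OLE: 316 − 316 = 0 days.

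**Distance from the end of capture to the end of AE recording**

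| Case | Formula | Days |
|---|---|---|
| Double-blind, nominal | 197 − 141 | 56 |
| OLE, nominal | 372 − 316 | 56 |
| Double-blind, shortest, ±7 on both visits | (197 − 7) − (141 + 7) | 42 |
| Double-blind, longest, ±7 on both visits | (197 + 7) − (141 − 7) | 70 |

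With only ±3 days on dose 6, the double-blind range narrows to (197 − 7) − (141 + 3) = 46 and (197 + 7) − (141 − 3) = 66 days.

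**What applies to an uncomplicated pregnancy beginning on Day 160 in a subject not in the OLE**

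- Opening sentence of 13.7.3: outside capture (160 > 141).
- Subject and partner instructions in 13.7.3: to be reported, since the study runs at least to Day 197.
- Inclusion criterion 9, for a partner: to be reported.
- Investigator duty in 13.7.3: to be reported within 24 hours of awareness.
- AE window: open, but this is not an AE.

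One provision excludes the pregnancy and three may require a report. Nothing in either document says which prevails.

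**Distance to the contraception period**

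Inclusion criterion 9 requires contraception to the end of the study or for 120 days after the last dose, whichever is longer. The 120 days end on Day 141 + 120 = 261, or Day 316 + 120 = 436. That is 261 − 197 = 64 and 436 − 372 = 64 nominal days beyond the AE window.

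**The case against.** The strongest reply is that later pregnancies are already reached. The investigator's duty has no end day, and subjects are told to report throughout the study. Inclusion criterion 9 repeats this for partners. Sites must ask about changes in health status at Days 169 and 197 (sections 12.11 and 12.12). Congenital abnormalities have their own SAE duty, also without an end day. Contraception is mandatory over the same weeks, so few events are expected. All of this stands, and it limits the consequence. It does not remove the opening sentence, which still states a different end to the period.

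Four stronger readings are tempting, and the documents do not support them.

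- **Pregnancies after Day 141 cannot be reported.** The undated investigator duty shows otherwise.
- **Capture must run for 120 days after the last dose.** No provision ties capture to the contraception period. The 5 half-lives (up to 4 months) in exclusion criterion 15 concern live vaccines. The consent form is not available here and may carry an instruction of its own.
- **Subjects who receive less drug get more post-dose capture.** Some may, because capture runs to ET or Day 141. But ET can fall before or after the usual 28 (±3) days (Table 1, note 32), and section 14.2 only encourages those who stop drug to stay on study. No fixed number of days follows.
- **Capture should extend to the last Extended Follow-Up visit, like SAE recording.** Sections 11.2.8 and 12.14 limit those visits to blood counts, SAEs and AESIs, so that change would create a new conflict.

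**Conclusion.** The opening sentence of 13.7.3 contradicts the reporting duties later in the section and the partner instruction in inclusion criterion 9. It also closes 56 nominal days before the AE window in both periods, or 42 to 70 days in the double-blind period with the accepted visit windows. For subjects who complete dosing and the study, it provides no post-dose capture of uncomplicated pregnancies. The conclusion is limited to those subjects because someone who receives dose 6 and then terminates early can be read as captured to ET.

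The possible harm is incomplete pregnancy-exposure data if sites follow the opening sentence literally. The documents give no figure from which to estimate how many pregnancies this concerns. No efficacy result, TEAE table or stopping rule depends on it. Severity is minor, and confidence in the inconsistency is high because it rests on the protocol's own text and day numbers.

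**What to change.** Amend the opening sentence of 13.7.3 so that pregnancies in subjects and partners are captured from first exposure through the Day 197 visit, the Day 372 visit for OLE subjects, or ET. This matches the AE window. For subjects in Extended Follow-Up, the undated investigator duty would continue to apply, as it does now.

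The cost is one sentence in the next amendment, with the written IRB approval that section 17.1 requires. No visit or test is added.

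Optionally, ask subjects at the last visit to report pregnancies up to 120 days after the last dose, in line with inclusion criterion 9. For completers without Extended Follow-Up this covers about 64 further nominal days. The downside is a longer reporting duty for sites after the final visit. It is an improvement to consider and is not needed to remove the contradictory Day 141/316 cut-off.
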